9.6. Data management

A data management plan will be created before data collection begins and will describe all functions, processes, and specifications for data collection, cleaning, and validation. The eCRFs will include programmable edits to obtain immediate feedback if data are missing, out of range, illogical or potentially erroneous. Concurrent manual data review will be performed based on parameters dictated by the plan. Ad hoc queries will be generated within the electronic data capture (EDC) system and followed up for resolution. Data quality will be enhanced through a series of programmed data quality checks that automatically detect out of range or anomalous data

High data quality standards will be maintained, and processes and procedures utilized to repeatedly ensure that the data are as clean and accurate as possible when locked for analysis.

9.6.1. Case report forms (CRFs)/Data collection tools (DCTs)/Electronic data record

As used in this protocol, the term CRF should be understood to refer to either a paper form or an electronic data record or both, depending on the data collection method used in this study.

A completed CRF is required for each included participant. The completed original CRFs are the sole property of Pfizer and should not be made available in any form to third parties, except for authorized representatives of Pfizer or appropriate regulatory authorities, without written permission from Pfizer. IQVIA shall ensure that the CRFs are securely stored at the IQVIA data warehouse in encrypted electronic form and will be password protected or secured in a locked room to prevent access by unauthorized third parties.

IQVIA has ultimate responsibility for the collection and reporting of all data entered on the CRFs as required and ensuring that they are accurate, authentic/original, attributable, complete, consistent, legible, timely (contemporaneous), enduring, and available when required. The CRF serves as the source document. Any corrections to entries made in the CRFs must be dated, initialed, and explained (if necessary) and should not obscure the original entry.

9.6.2. Record retention

To enable evaluations and/or inspections/audits from regulatory authorities or Pfizer, IQVIA agrees to keep all study-related records. The records should be retained by IQVIA according to local regulations or as specified in the vendor contract, research agreement, whichever is longer. IQVIA must ensure that the records continue to be stored securely for so long as they are retained.

If IQVIA becomes unable for any reason to continue to retain study records for the required period, Pfizer should be prospectively notified. The study records must be transferred to a designee acceptable to Pfizer.

Study records must be kept for a minimum of 15 years after completion or discontinuation of the study, unless IQVIA and Pfizer have expressly agreed to a different period of retention

via a separate written agreement. Record must be retained for longer than 15 years if required by applicable local regulations.

IQVIA must obtain Pfizer's written permission before disposing of any records, even if retention requirements have been met.

9.7. Data analysis

The study population of Pfizer-BioNTech COVID-19 mRNA vaccine recipients will be described in terms of demographic characteristics (age, gender, ethnicity, occupation) and medical history characteristics outlined in [Section 9.4.1](#). Vaccination characteristics, including number of doses received and interval between doses, will also be described.

The incidence rates of medically attended safety events of interest and corresponding 95% Poisson exact confidence intervals (95% CI) will be estimated in the primary safety dataset of participants who enroll within 2 days of vaccination. Rates will also be estimated for the overall study population and within subcohorts of interest such as pregnant vaccine recipients, immunocompromised participants, and within age-categories.

A final analysis will also be conducted for the following subcohorts of interest, given the potential for mixed exposure:

1. **Pfizer-BioNTech vaccine only**: all participants who only receive Pfizer-BioNTech COVID-19 mRNA vaccine(s), and no other COVID-19 vaccine(s), prior to index date and during their follow-up period.
2. **Heterologous vaccination**:
 - a) **Pfizer-BioNTech booster(s) only**: all participants who received only Pfizer-BioNTech COVID-19 mRNA vaccine dose(s) as booster dose(s) during the study period, but where the primary vaccine course (prior to index date) was non-Pfizer-BioNTech.
 - b) **Heterologous primary course**: all participants who received Pfizer-BioNTech COVID-19 mRNA vaccine as a first dose at index date, and then received a non-Pfizer-BioNTech second dose during their follow-up period. No booster doses were received.
 - c) **Other combination heterologous vaccine course/booster**: all participants with a heterologous primary course and/or heterologous booster dose(s), who do not fit the criteria for inclusion in subcohorts 2(a)-(b) above.

It is anticipated that rates will be reported for the following intervals, overall and for each of the subcohorts of interest:

- Follow-up at weeks 1, 2, 4, 6 and 8 following a Pfizer-BioNTech COVID-19 mRNA vaccine dose,
- Quarterly follow-up following a Pfizer-BioNTech COVID-19 mRNA vaccine dose (until 24 months following index date vaccine dose, or end of study, whichever occurs first).

[figure not shown]
Time at risk will be assessed from the Pfizer-BioNTech COVID-19 mRNA vaccine dose until the subsequent follow-up time point or until the next Pfizer-BioNTech COVID-19 mRNA vaccine dose received, death, withdrawal of consent, loss to follow-up, 24 months or end of study period, whichever occurs first. Sensitivity analysis may be conducted with censoring at any COVID-19 vaccine dose received.

All cases of reported laboratory confirmed COVID-19 in the study population will be described by the Brighton Collaboration “Vaccine-associated Enhanced Disease” Working Group case definitions for COVID-19 VAED.

Counts of newly reported medically attended safety events of interest and counts of vaccinated participants will be summarized as per the intervals above. Counts will be summarized by whether medical validation of the event was possible, or not.

To answer the first secondary objective, the observed rate of events will be compared with expected rates using the Observed to Expected (OE) analysis approach (6). The core principle of OE analysis is to estimate the expected number of coincidental cases of medically attended safety events of interest, under the assumption of no association with the vaccine. Expected numbers are then compared with the number of cases actually reported in vaccine recipients. The expected background incidence rate of a particular safety event of interest is the number of new cases occurring naturally in the population, expressed in person-time. The comparison of OE number of medically attended safety events of interest will be expressed as the ratio of the observed over the expected: an OE ratio equal to 1 means that the observed number of cases equals the expected number of cases, whereas an OE ratio greater than 1 signals an excess of risk in the vaccinated population. The statistical uncertainty of the OE analysis will often be driven by the observed number of cases, which are often rare events. To deal with this statistical uncertainty, a 95% Poisson exact confidence interval (95% CI) will be calculated (7). If the lower limit of the 95% CI of the OE ratio is greater than 1, the observed value is considered significantly higher than expected (Figure 2, case [a]). If the upper limit of the 95% CI of the OE ratio is lower than one, the observed value is considered significantly lower than expected (Figure 2, case [b]). If the 95% CI contains 1, then the observed and the expected numbers will not be considered significantly different (Figure 2, case [c]).

[figure not shown]
Figure 2. Observed to Expected (OE) Ratios and 95% Confidence Intervals (CIs)

Expected background rates of safety event of interest will be obtained from the EMA-funded COVID-19 vaccine monitoring ACCESS program (8). The ACCESS program is generating background incidence rates of AESI for COVID-19 vaccines over the period 2017 to 2020 from 10 healthcare databases in 7 European countries (8). The analysis in this study will include age-categories in line with the published incidence rates from ACCESS (18-29; 30-39; 40-49; 50-59; 60-69; 70-79; 80+). For safety event of interest which are not expected to be investigated through the ACCESS program, expected rates will be obtained from historical or concurrent rates reported in the literature, including from reports or data available through health authorities or large databases where possible (9, 10). This OE analysis has been favorably compared with other methods for active surveillance of vaccine safety (10).

For selected endpoints, such as those with acute onset and a defined risk window (listed in Annex 4), a SCRI analysis will be implemented if case counts are sufficient. SCRI analysis, described by Farrington (11, 12, 13), compares incidence rates between “risk” and “control” time periods (intervals) among vaccinated individuals, under the assumption that the risk of onset of a safety event of interest on a day during the risk period is the same as that on a day during the control period. The risk interval is a biologically plausible window of time following a vaccine when a safety event of interest could be caused by the vaccine (Figure 3).

Figure 3. Self-Controlled Risk Interval (SCRI) analysis: defining risk and control intervals

090177e1991e3913\Approved\Approved On: 18-Jan-2022 22:29 (GMT)

Medically attended safety events of interest caused by the vaccine would be expected to cluster shortly after vaccination, and therefore medically attended safety events of interest caused by the vaccine would be expected to have higher incidence rates in the risk interval than in the control interval for an individual. If medically attended safety events of interest are found to cluster in the pre-defined risk window shortly after vaccination, this would suggest – though not confirm – a causal association. The comparison of the risk to the control windows can be expressed as the ratio of the safety event of interest incidence rate on the risk interval over the 1 on control interval: an incidence rate ratio (IRR) of 1 means that the incidence rate is the same in both intervals, whereas an IRR greater than 1 signals an excess of risk in the risk interval (shortly after vaccination). If the lower limit of the 95% CI of the IRR is greater than 1, the incidence rate in the risk interval is considered significantly higher than that in the control interval; if the upper limit of the 95%CI of the IRR is lower than 1, the incidence rate in the risk interval is considered significantly lower than that in the control interval; if the 95%CI contains 1, the incidence rates are not considered significantly different between the 2 intervals. This methodology has been widely used in vaccine safety studies and has been shown to be a powerful and practical method of assessing vaccine safety, with the self-controlled design implicitly controlling for fixed (non time-varying) confounding factors (e.g. sex, ethnicity) (13, 14).

The SCRI analysis will be carried out as part of the final analysis following database lock. Risk intervals for each safety event of interest will be sourced from published literature. The IRR of medically attended safety events of interest occurring in the risk interval versus the control period will be estimated by fitting a conditional Poisson regression model (15). For each safety event of interest, analyses will be restricted to individuals who experience that safety event of interest either during the risk or the control interval. Sensitivity analysis may be conducted considering different assumptions of the risk and control window lengths.

Table 5 depicts the planned analyses related to each study objective.

Table 5. Planned analysis by study objective

Objective	Outcome of interest	Planned analysis

Primary study objective:
 
Estimate the real-world incidence of medically attended safety events of interest and other clinically significant events among individuals vaccinated with the Pfizer-BioNTech COVID-19 mRNA vaccine after approval in the EU.
	
Medically attended safety events of interest, and other clinically significant events
	
Incidence rates per 10,000 person-years and corresponding 95% Poisson exact CI. Incidence rates precision estimates as provided in Section 9.5.

Secondary objective:
 
Evaluate whether the vaccine recipients experience increased risk of medically attended safety events of interest post-vaccination, via comparison with expected background rates and, as feasible, by self-controlled risk interval (SCRI) analysis.
	
Medically attended safety events of interest
	
OE analysis: Safety event of interest (observed) incidence rates in cohort of study participants compared to background (expected) incidence rates, obtained from the EMA-funded COVID-19 vaccine monitoring ACCESS program or, if unavailable, from historical or concurrent rates reported in the literature.
 
SCRI analysis: Incidence rate ratio (IRR) of medically attended safety events of interest occurring in the risk interval versus the control period, estimated by conditional Poisson regression models. Sensitivity analysis for SCRI: considering different lengths of the risk and control intervals.

090177e1991e3913\Approved\Approved On: 18-Jan-2022 22:29 (GMT)

Table 5. Planned analysis by study objective

Objective	Outcome of interest	Planned analysis

Secondary objective:
 
Estimate the incidence rates of medically attended safety events of interest among sub-cohorts of interest such as pregnant vaccine recipients, immunocompromised participants, and stratified by age.
	
Medically attended safety events of interest
	
Incidence rates per 10,000 person-years and corresponding exact Poisson 95%CI*:
 
 • Among sub-cohort of pregnant vaccine recipients, • Among sub-cohort of immunocompromised participants, • Stratified by age: 18-29; 30-39; 40-49; 50-59; 60-69; 70-79; 80 and above.

European Union (EU); 95% Poisson exact confidence intervals (95% CI); self-controlled risk interval (SCRI); incidence rate ratio (IRR).

*analysis presented by subcohorts of Pfizer-BNT COVID-19 mRNA vaccine, or heterologous vaccination courses, in the final report.

Detailed methodology for summary and statistical analyses of data collected in this study will be documented in a SAP, which will be dated, filed, and maintained by the sponsor. The SAP will include the pre-defined expected background rates of medically attended safety events of interest for the OE analysis, including those published by the ACCESS program, and the risk intervals for medically attended safety events of interest anticipated to be included in the SCRI analysis if case counts are sufficient. Sensitivity analyses will also be detailed in the SAP.

The SAP may modify the plans outlined in the protocol; any major modifications of primary endpoint definitions or their analyses would be reflected in a protocol amendment.

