9.2.1. Inclusion criteria

Participants must meet all of the following inclusion criteria to be eligible for inclusion in the study:

1. Participant's age is 18 years and above, and in accordance with the approved product label of the country where the study is conducted.
2. Enrolment within 5 days of receipt of any dose (i.e. first, second, or any subsequent booster dose) of the Pfizer-BioNTech COVID-19 mRNA vaccine.

Note:

Heterologous primary vaccination (two different COVID-19 vaccines [different manufacturers] received for the first and second doses of a primary [initial] course) and heterologous boosting (a third dose of a different manufacturers COVID-19 vaccine as a booster 3 to 6 months after a primary vaccination course) are now commonplace.

Individuals receiving heterologous booster doses are allowed to enroll in this study, if the booster dose received is the Pfizer-BioNTech COVID-19 mRNA vaccine. However, if a participant is enrolling at second Pfizer-BioNTech COVID-19 mRNA vaccine dose, the first dose received must have also been the Pfizer-BioNTech COVID-19 mRNA vaccine². If a participant is enrolling at second or booster dose of Pfizer-BioNTech COVID-19 mRNA vaccine, the participant must be able to provide the date and manufacturer of all previous COVID-19 vaccine doses received in order to be eligible for inclusion.

3. Adult participants willing to provide informed consent according to local regulations and complete all study procedures in accordance with the protocol, including consent for the study team to contact the treating HCP or healthcare facility to obtain additional information related to safety events reported by the participant.

² Including patients receiving the Pfizer-BioNTech COVID-19 mRNA vaccine as their second dose, who have not received the Pfizer-BioNTech COVID-19 mRNA vaccine as their first dose, would result in any vaccine effects being difficult to distinguish between manufacturers. No such restrictions are placed upon participants enrolling at booster doses, as the time window between doses is anticipated to be longer, with reduced likelihood of overlapping risk intervals.

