9.2.3. Recruitment and retention

After vaccination, all eligible individuals will be invited to participate in the study within 5 days of vaccination, and will be fully informed about the nature and objectives of the study, as well as the sharing of data relating to the study. The study recruitment strategy will encourage enrolment within 2 days of vaccination. Individuals will be provided adequate time to have questions answered prior to consenting to participate. Further details of the consent process are detailed in [Section 9.2](#). All participants will be able to withdraw consent at any time via the app, or at any follow-up point via telephone.

Participants will be followed up at pre-specified, regular intervals. As described in [Section 9.1](#), participants will have the opportunity to choose their preferred method of follow-up. Reminders will be sent if a participant fails to submit follow-up data via the app, and follow-up calls will be attempted if a participant fails to submit follow-up data via telephone. If the participant is non-responsive to follow-up reminders or telephone calls, follow-up with a secondary contact and the participant's primary care will be attempted, in order to determine whether non-response is due to a safety event of interest.

For participants who request to participate via the app, the following reminder schedule will be implemented:

For the weekly and bi-weekly questionnaires completed as needed after each dose:

- Two digital reminders,
- If digital reminders are ignored by the participant, the IQVIA call center will call to remind the participant to complete the questionnaire, as well as offer a Toll Free Number (TFN) if the participant would prefer to complete the questionnaire over the phone by talking to an agent,
- If no response to the call center or call-in to TFN, the named secondary contact provided by the participant will be contacted,

For the quarterly questionnaires after each dose:

- Three digital reminders,
- If digital reminders are ignored by the participant, the IQVIA call center will call to remind the patient to complete the questionnaire, as well as offer a TFN if the participant would prefer to complete the questionnaire over the phone by talking to an agent,
- If no response to the call center or call-in to TFN, the named secondary contact provided by the participant will be contacted,

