9.5. Study size

The primary objective of this study is to quantify the incidence of medically attended safety events of interest by estimating their incidence rates per 10,000 person-years, calculated as the number of participants experiencing the event after receiving a dose of the Pfizer-BioNTech COVID-19 mRNA vaccine during the person-time at risk (numerator) divided by the total person-time at risk (denominator).

The target for enrolment will be approximately 13,334 participants (vaccine recipients). Table 4 provides illustrative examples of expected margin of error ([width of confidence interval/2]) for different incidence rates per 10,000 person-years. The margin of error was calculated for a range of attrition rates (25%, 40%, and 55%) for illustrative purposes.

Table 4. Margin Of Error Scenarios For Targeted Sample Size And Different Incidence Rates Over A 24-Month Follow-Up Period

Target n	Attrition rate assumption	Expected n who complete 24 months follow-up	Incidence rate (per 10,000 person-years)	95% Confidence intervals (exact) according to different incidence scenarios	Margin of error
13,334	25%	10,000	1	[0, 3]	1.5
			5	[3, 9]	3.0
			10	[6, 15]	4.5
			50	[41, 60]	9.5
			250	[230, 271]	20.5
			500	[472, 530]	29.0
			2500	[2436, 2565]	64.5
			5000	[4910, 5092]	91.0
	40%	8,000	1	[0, 4]	2.0
			5	[2, 10]	4.0

Table 4. Margin Of Error Scenarios For Targeted Sample Size And Different Incidence Rates Over A 24-Month Follow-Up Period

Target n	Attrition rate assumption	Expected n who complete 24 months follow-up	Incidence rate (per 10,000 person-years)	95% Confidence intervals (exact) according to different incidence scenarios	Margin of error
			10	[5, 17]	6.0
			50	[39, 64]	12.5
			250	[223, 279]	28.0
			500	[462, 540]	39.0
			2500	[2414, 2588]	87.0
			5000	[4878, 5124]	123.0
	55%	6,000	1	[0, 6]	3.0
			5	[1, 12]	5.5
			10	[5, 20]	7.5
			50	[37, 68]	15.5
			250	[218, 286]	34.0
			500	[454, 549]	47.5
			2500	[2396, 2607]	105.5
			5000	[4853, 5151]	149.0

The 95% confidence intervals are derived using the (exact) Clopper and Pearson method.

Calculations were done in R Version 4.0.2.

Further analyses described in [Section 9.7](#) for secondary endpoints will be exploratory in nature and will not involve formal hypothesis testing. The statistical analysis plan (SAP) will expand the statistical methods mentioned in [Section 9.7](#) of this protocol.

090177e1991e3913\Approved\Approved On: 18-Jan-2022 22:29 (GMT)

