9.9. Limitations of the research methods

This is a non-interventional, multinational, multi-center PASS to further document the safety profile of participants vaccinated with the Pfizer-BioNTech COVID-19 mRNA vaccine. Participants will be followed for up to 24 months after their vaccine dose.

The time frame of 24 months post-vaccination will allow evaluation of the long-term safety profile of the Pfizer-BioNTech COVID-19 mRNA vaccine in a real-world population. To reduce the likelihood of sampling bias, broad inclusion criteria and consecutive participant selection will be applied.

Recruiting participants soon after vaccination is important to prevent over-representation of participants who elect to enroll only after experiencing an event. The study recruitment strategy will encourage enrolment within 2 days of vaccination, but in consideration of the enrolment goal of up to 10,000 participants, diverse and changing local vaccine roll-out strategies, and to provide potential participants enough time to inform themselves fully before consenting, only enrollment within 5 days of vaccination will be eligible.

There is potential for loss to follow-up prior to study completion. To reduce the likelihood of loss to follow-up, active monitoring of participants will be employed. For participants who discontinue the study prematurely, the reason(s) for discontinuation will be recorded. The sponsor will aim to minimize missing information by the measures outlined in [Section 9.7.1](#).

There is also the potential for recall bias where participants may not remember or report events that occurred in between the questionnaire intervals. This is likely to be minimized by focusing on serious events and hospitalizations.

As participants may receive multiple vaccine doses during the study period, and may receive different types of COVID-19 vaccine, attributing outcomes to the relevant exposure period may be challenging. However, this will be mitigated through the collection of data on other vaccines (including date and manufacturer), including those received prior to the index date dose (e.g. to facilitate exclusion of participants who received the Pfizer-BioNTech COVID-19 mRNA vaccine as their second dose, who *did not* receive the same vaccine as their first dose), as well as through sensitivity analysis.

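### Table 4's precision belongs to all 13,334 enrolees, not to the 2-day primary safety dataset, and the observed-to-expected analysis names no analysis set

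*Protocol*

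**What the plan says.** Protocol Section 9.2.1 admits participants on "Enrolment within 5 days of receipt of any dose (i.e. first, second, or any subsequent booster dose"). Section 9.2.3 adds: "The study recruitment strategy will encourage enrolment within 2 days of vaccination". Neither section requires 2-day enrolment, and no section gives a target or an expected share for it.

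Section 9.7 states that the primary incidence rates "will be estimated in the primary safety dataset of participants who enroll within 2 days of vaccination". The wider population comes second: "Rates will also be estimated for the overall study population and within subcohorts of interest".

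Section 9.5 sizes the study on everyone enrolled: "The target for enrolment will be approximately 13,334 participants (vaccine recipients"). Table 4 then gives margins of error for that target under 25%, 40% and 55% attrition. In Table 5 the row for the primary objective reads "Incidence rates precision estimates as provided in Section 9.5".

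For the OE comparison, Table 5 refers to "observed) incidence rates in cohort of study participants compared to background (expected) incidence rates". The OE text of Section 9.7 speaks only of vaccine recipients. Neither place uses the defined term for the 2-day dataset. Section 9.9 explains why prompt recruitment matters: to "prevent over-representation of participants who elect to enroll only after experiencing an event".

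**The concern.** The primary estimate comes from a subset, while its stated precision comes from the whole. The two agree only if nobody enrols on days 3 to 5. Section 9.9 keeps the 5-day window open because of the enrolment goal, changing vaccine roll-out and time to consent, so some enrolment on those days is to be expected. A reader of Table 5 would then credit the primary rates with more precision than the design delivers.

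The second issue is where the protection against selection applies. The 2-day restriction guards against people who join because something has already happened to them. The OE ratio is the analysis most exposed to that error, because such enrolees add observed cases without adding expected ones, and Section 9.7 attaches a rule for calling a ratio significantly raised. Yet the OE text does not say whether the restriction applies.

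**Working it through.** **Inputs.** From the protocol: 13,334 enrolled, 10,000 completers, 25% dropout, 24 months of follow-up, and the printed rows of Table 4 (Sections 9.2 and 9.5). Assumptions: dropouts contribute one year on average; f, the share enrolled within 2 days, is not given and is shown as a range.

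**Step 1: reproduce Table 4, 25% block.**

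Person-years = 13,334 × 0.75 × 2 + 13,334 × 0.25 × 1 = 20,001 + 3,333.5 ≈ 23,334.

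For a rate r per 10,000 person-years, expected events x = r/10,000 × person-years. The exact Poisson limits are χ²(0.025; 2x)/2 and χ²(0.975; 2x + 2)/2, each divided by person-years.

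At r = 250, x = 583.4 and the limits are 230.1 and 271.1; the table prints [230, 271] with margin 20.5. All eight rows of the block match. Counting only completers (20,000 person-years) gives [229, 273] at r = 250 and matches one row of eight. The block therefore uses the person-time of all enrolees. (The footnote names Clopper-Pearson, but those limits on the same person-years match five of eight rows. That is a separate point.)

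**Step 2: precision in the primary safety dataset.** Person-years become 23,334 × f. For all but small counts the margin scales by 1/√f: 1.05 at f = 0.9, 1.20 at 0.7 and 1.41 at 0.5. Exact Poisson half-widths per 10,000 person-years, 25% attrition:

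| Rate | f = 1 | f = 0.9 | f = 0.7 | f = 0.5 |
|---|---|---|---|---|
| 10 | 4.3 | 4.5 | 5.2 | 6.2 |
| 50 | 9.3 | 9.8 | 11.2 | 13.3 |
| 250 | 20.5 | 21.6 | 24.6 | 29.1 |
| 500 | 28.9 | 30.5 | 34.6 | 41.0 |

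Table 4 prints 4.5, 9.5, 20.5 and 29.0 for these rates because it halves the width of rounded limits. At rate 250 and f = 0.5 the result is 29.1 or 29.2, depending on whether the 291.7 expected events are rounded to 292.

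**Step 3: OE, illustration only.** Suppose that OE uses all 13,334 enrolees, that events before enrolment are counted, and that the only observed cases in week 1 are a few event-prompted enrolees.

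- Background 10 per 10,000 person-years: expected cases = 10/10,000 × 13,334 × 7/365.25 = 0.256. Three such enrolees give OE = 3/0.256 = 11.7, with exact lower limit 0.619/0.256 = 2.4.
- Background 5: expected cases = 0.128. Two such enrolees give a lower limit of 0.242/0.128 = 1.9.
- Background 10 over the full 23,334 person-years: expected cases = 23.3. Three extra cases (26 observed) give OE 1.11, 95% CI 0.73 to 1.63, so no signal.
- Background 10 over 90 days: expected cases = 10/10,000 × 13,334 × 90/365.25 = 3.29. Six observed give a lower limit of 0.67, so no signal.

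The effect is confined to short windows and small expected counts, and the numbers of event-prompted enrolees are assumed.

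**The case against.** **On precision.** Section 9.5 calls the examples in Table 4 illustrative, and no power claim rests on them. The protocol abstract expects people to be enrolled when they present for vaccination, which with the encouragement in Section 9.2.3 suggests a high 2-day share. At 90% the loss is about 5%. The 55% attrition block already prints wider margins (15.5 at rate 50, 34.0 at rate 250) than the 50% share would give. All of this bears on size and makes a large loss less likely. It does not remove the mismatch: Table 5 assigns the Section 9.5 figures to the primary objective, and the worse blocks are labelled as attrition, not as restriction to early enrolees.

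**On OE.** A reader might infer that the OE analysis is built on everyone enrolled within 5 days. The protocol does not say so. Table 5's mention of study participants may only be a contrast with background rates, and Section 9.7 has already tied the primary rates to the 2-day set. The SAP, which is not at hand, may name the set. A reader might also take the week-1 figures as showing that a false signal is likely. They do not: the abstract limits the comparison to events with enough cases, which may exclude counts of two or three, and Section 9.5 calls the secondary analyses exploratory, without formal testing. Nor is it settled that events before enrolment count. Section 9.3.1 collects events from enrolment, whereas Section 9.7 starts time at risk at the dose and the follow-up questionnaire in Annex 3 asks about care since vaccination. These objections stand. What remains is that the OE set is unnamed and that the most natural reading of Table 5 is all enrolees.

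**Conclusion.** The precision point holds. Table 4 describes the overall study population and overstates the precision of the primary safety dataset unless everyone enrols within 2 days. The margin is too narrow by about 5% at f = 0.9, 20% at f = 0.7 and a little over 40% at f = 0.5. These shares are assumptions, and the protocol's own recruitment wording favours the upper end. The reproduction rests on dropouts contributing one year on average, a convention that matches every row of the 25% block.

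The OE point holds only as an ambiguity. The protocol does not say which set the comparison uses. If it means all enrolees, it admits the selection that Section 9.9 wants to avoid, and in that case the error would run towards a raised ratio. Its size cannot be derived from the protocol.

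**What to change.** 1. In Section 9.5 and in the primary-objective row of Table 5, state that Table 4 describes the overall study population. Add margins for the primary safety dataset at stated assumed 2-day shares, for example 90%, 70% and 50%. The cost is a few table rows and a less favourable stated precision.
2. In the OE text of Section 9.7 and in Table 5, name the 2-day primary safety dataset as the main OE population and the 5-day population as the sensitivity analysis. This applies the rationale of Section 9.9 to the analysis that most needs it. The main OE analysis loses the person-time of day 3 to 5 enrolees, a fraction 1 − f, which the sensitivity analysis retains. If the 2-day set is already intended, one sentence is enough.

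Neither change affects eligibility, recruitment or data collection.
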